3.2 Key Definitions

The following definitions will be used:

- **Baseline:** The baseline value is defined as the last available valid (quantifiable continuous or categorical value), non-missing observation for each participant prior to first study drug administration. Repeat and unscheduled assessments will be included in the derivation of the baseline values.

For HBsAg, ALT, AST, ALP, and total Bilirubin (TBL), the baseline value is defined as the average of screening and day 1 pre-dose.

For HBeAg, the Baseline value is value taken at screening visit.

- **Change from Baseline:** The change from baseline value is defined as the difference between the result collected/derived at a post-baseline visit/time point and the baseline value.

The change from baseline value at each post-baseline visit/time point will be calculated for all continuous parameters using the following formula:

$$\text{Change from Baseline Value} = \text{Result at Visit/Time Point} - \text{Baseline Value}$$

The change from baseline value will only be calculated if the specific post-baseline visit/time point result and the baseline value for the parameter are both available and will be treated as missing otherwise.

- **Percent Change from baseline:** The percent change from baseline at each post-baseline visit/time point will be calculated for all continuous parameters using the following formula:

$$\% \text{ Change from Baseline} = 100 \times [(\text{Post-Dose Visit Value} - \text{Baseline}) / \text{Baseline}]$$

- **Study day:** The study day of an event is defined as the relative day of the event starting with the date of the first study drug administration (reference date) as Day 1 (there will be no Day 0).

The study day of events occurring before the first study drug administration will be calculated as:

$$\text{Study Day} = (\text{Date of Event} - \text{Date of First Study Drug Administration})$$

For events occurring on or after Day 1, study day will be calculated as:

$$\text{Study Day} = (\text{Date of Event} - \text{Date of First Study Drug Administration}) + 1$$

Study days will only be calculated for events with complete dates and will be undefined for events that are 'Ongoing' at the end of the study.

Relative days compared to an alternative reference point will be calculated similarly, but the alternative starting reference start date will be used instead of the date of the first study drug dosing.

Please note that for this study, first study drug dosing is considered to occur on Day 1.

- **Breakthrough:** Quantifiable HBV DNA increase of $\geq 1 \log_{10}$ HBV DNA copies/mL above LLOQ.
- **Lower limit of quantification (LLOQ):** HBV DNA results i.e HBsAg < LLOQ will be reported as either <LLOQ/Detected (i.e. LLOQ/TD) or <LLOQ/Target Not Detected (i.e. LLOQ/TND), both are considered LLOQ. HBsAg loss rates will be further subdivided accordingly.

- HBsAg decline: Change from Baseline in HBsAg on the log₁₀ scale. Negative values indicate a decline.
- HBsAg loss: Patients with HBsAg < LLOQ/TND.
- HBsAg responder A: A decrease from baseline ≥ 1.0 on the log₁₀ scale, i.e. a change from baseline of ≤ -1.0 . HBsAg results <LLOQ/Target Not Detected will be reported as 0.015 [$\log_{10}(0.015) = -1.852$] and HBsAg < LLOQ/Target Detected will be reported as midpoint between LLOQ/Target Not Detected and LLOQ/Target Detected, i.e. 0.04IU/mL = $\log_{10}(0.04) = -1.4$. Also, HBsAg above LLOQ will be reported as the raw data is reported.
- HBsAg responder B: A decrease from baseline ≥ 0.5 on the log₁₀ scale, i.e. a change from baseline of ≤ -0.5 . HBsAg results <LLOQ/Target Not Detected will be reported as 0.015 [$\log_{10}(0.015) = -1.852$] and HBsAg < LLOQ/Target Detected will be reported as midpoint between LLOQ/Target Not Detected and LLOQ/Target Detected, i.e. 0.04IU/mL = $\log_{10}(0.04) = -1.4$. Also, HBsAg above LLOQ will be reported as the raw data is reported.
- HBsAg Relapse Rate: Patients who became negative (HBsAg<LLOQ), then increased with HBsAg > LLOQ. HBsAg results <LLOQ/Target Not Detected will be reported as 0.015 [$\log_{10}(0.015) = -1.852$] and HBsAg < LLOQ/Target Detected will be reported as midpoint between LLOQ/Target Not Detected and LLOQ/Target Detected, i.e. 0.04IU/mL = $\log_{10}(0.04) = -1.4$. Also, HBsAg above LLOQ will be reported as the raw data is reported.
- Virologic failure: Patients with a confirmed quantifiable HBV DNA increase of $\geq 1 \log_{10}$ HBV DNA copies/mL above LLOQ. HBV DNA results < LLOQ/Target Not Detected will be reported as 10 [$\log_{10}(10) = 1$] and HBV DNA < LLOQ/Target Detected will be reported as midpoint between LLOQ/Target Not Detected and LLOQ/Target Detected, i.e. 20IU/mL = $\log_{10}(20) = 1.3$. Also, HBV DNA above LLOQ will be reported as the raw data is reported.
- HBV-pgRNA decline: Change from Baseline in HBV-pgRNA on the log₁₀ scale. Negative values indicate a decline.
- HBcrAg decline: Change from Baseline in HBcrAg on the log₁₀ scale. Negative values indicate a decline.
- Prior Medications: Prior medications are defined as any medication where the use was stopped prior to the first administration of the study medication.
- Concomitant Medications: Concomitant medications are defined as any medication (other than the study drug) that was used at least once after the first administration of the study drug. Medications that were stopped on the same date as the first study drug administration will be defined as concomitant medications. If a clear determination cannot be made (partial medication end dates) the medication will be classified as concomitant
- Treatment Emergent Adverse Events (TEAEs) are defined as adverse events that occurred following the first administration of study medication.

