### 3. Study Plan

#### 3.1. Description of Overall Study Design and Plan

This is a prospective, multi-centre, randomized, double-blind, placebo controlled, Phase 2a experimental study of oral FXR modulator EYP001a/placebo combined with NA in virologically suppressed CHB patients to improve functional cure rates.

---

 Breakthrough samples will be further assessed for resistance assessments, including both for the nucleos(t)ide analogue as well as for EYP001a (e.g., sequence analysis of FXR response elements in HBV genome). Details will be described in the Laboratory manual.

 HBV DNA results <LLOQ will be reported as either <LLOQ/Detected (i.e. LLOQ/TD) or <LLOQ/Target Not Detected (i.e. LLOQ/TND), both are considered LLOQ.

In total 49 eligible patients will be enrolled and randomized at approximately 14 study sites. Patients will be randomized prior to study drug (EYP001a or placebo and NA) administration on Day 1 in the ratio of 3:1 into 2 arms:

- **Experimental Arm:** EYP001a 200 mg QD + NA daily (37 patients)
- **Control Arm:** Placebo + NA daily (12 patients)

[figure not shown]
Patients will also be stratified per HBeAg status, based on medical history HBeAg value or established during screening, to obtain a balanced randomization to both study arms.

The maximum total engagement duration for eligible patients in this study is up to 370 days: 90 days screening, 112 days (16 weeks) treatment period and 168 days (24 weeks) follow-up.

Patients enrolled in the study will be assessed as outpatients. Patient screening will occur no more than 90 days prior to the Day 1 visit. Eligible patients will undergo further assessments on Day 1 to qualify for study drug administration on Day 1.

A diagrammatic representation of the study design is presented in [Figure 7](#):

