#### **8.1.1. Recording of Adverse Events**

All AEs during the course of the trial will be reported in the appropriate section in the eCRF. The investigator will give his or her opinion as to the relationship of the adverse event to the investigational product. The Investigator should attempt to establish a diagnosis of the AE based on signs, symptoms, and/or other clinical information. In such cases, the diagnosis should be documented as the AE verbatim term rather than individual signs/symptoms.

All AEs regardless of relationship to the study drug during the period starting from the time the participant signed the ICF through 7 days after the last study drug dose will be recorded in the eCRF.

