### 8.2.2. Reporting of Serious Adverse Events

All SAEs regardless of relationship to the study drug during the period starting from the time the patient signed the ICF through 7 days after the last study drug dose, will be

recorded in the eCRF. Once the Investigator becomes aware of an SAE, he/she must report the SAE to the Sponsor safety representative within 24 hours of knowledge of the event.

Safety Contact Information:

Pharmalex:

[contact]

[contact]

Email: [contact]

A written SAE report must include a full description of the event including the below parameters (include any protocol specific requirements):

- Diagnosis or description of event
- Onset date
- Severity assessment
- Causal relationship to the investigational product
- Assessment of seriousness of the event
- Corrective treatment administered for the SAE
- Action taken related to study drug include the following: dose interruption, dose delay, dose reduction, or study drug discontinuation
- Outcome of event and end date

Follow-up information for SAEs and information on non-serious AEs that become serious should also be reported to Sponsor Safety representative within 24 hours of receipt of follow-up information.

The Investigator must update the SAE form and submit any supporting documentation (eg, patient discharge summary or autopsy reports) to the ENYO safety designee via fax or email.

The Investigator is responsible for reporting all SAEs to the appropriate Institutional Review Board/Institutional Ethics Committee (IRB/IEC) in accordance with local laws and regulations. The Investigator is responsible for maintaining documentation in the study file that indicates the IRB/IEC has been properly notified.

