2. PROJECT OVERVIEW

2.1 Study Design

This is a prospective, multi-centre, international randomized, double-blind, placebo controlled, Phase 2a experimental study of oral FXR modulator EYP001a/placebo combined with Nucleos(t)ide analogues (NA) in virologically suppressed CHB patients to improve functional cure rates.

In total 49 eligible patients will be enrolled and randomized at approximately 14 study sites in 4 countries. Patients will be randomized prior to study drug (EYP001a or placebo and NA) administration on Day 1 in the ratio of 3:1 into 2 arms:

[figure not shown]
- Experimental Arm: EYP001a 200 mg once daily (QD) + NA daily (37 patients)
- Control Arm: Placebo + NA daily (12 patients)

Patients will also be stratified per HBeAg status, based on medical history HBeAg value or established during screening, to obtain a balanced randomization to both study arms.

The maximum total engagement duration for eligible patients in this study is up to 370 days: 90 days screening, 112 days (16 weeks) experimental treatment period and 168 days (24 weeks) follow-up on NA standard of care therapy (SOC) only.

Patients enrolled in the study will be assessed as outpatients. Patient screening will occur no more than 90 days prior to the Day 1 visit. Eligible patients will undergo further assessments on Day 1 to qualify for study drug administration on Day 1.

Figure 1: Study Design

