2.2.2 Secondary objective(s)

The secondary objectives of this study are:

- To establish the effect of EYP001a on top of NA on HBsAg responder rate at the end of the 16-week EYP001a treatment and at 24-week of follow-up (Week 40).
- To establish the effect of EYP001a on top of NA on HBsAg loss rate at the end of the 16-week EYP001a treatment and at 24-week of follow-up (Week 40).
- To establish the Hepatitis B virus (HBV) virologic failure rate (breakthrough) during the 24-weeks follow-up period after stopping EYP001a with ongoing NA.
- To determine HBV viral response, HBV Pg/Precore Ribonucleic Acid (pgRNA), Hepatitis B core-related antigen (HBcrAg) and Hepatitis B Surface e-Antigen (HBeAg), Antibody to Hepatitis B e

antigen (Anti-HBe) and Antibody to Hepatitis B surface antigen (Anti-HBs) at the end of the 16-week EYP001a treatment and Week 40 of follow-up.

- To explore the safety profile of EYP001a treatment in combination with NA.
- To determine the plasma concentration of EYP001a and pharmacodynamic (PD) markers (plasma C4 (7 α -hydroxy-4-cholesten-3-one)), fibroblast growth factor (FGF) 19 and BAs.

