13.1 Adverse Events

All AEs including will be coded using MedDRA. All AE summaries will be restricted to TEAEs only. Summary tables will include the number of participants (%) experiencing an event and the number of events. Participants will be counted only once for each SOC and PT level (categorical descriptive analysis).

AE and SAE will be analysed taking into account any identified subject with Sars-Cov2 infection during and post-pandemic measures phases. Such an analysis will be operated through the independent Data Monitoring Committee (DMC).

The TEAE summaries will include:

- Overall summary of TEAEs.
 - Number of TEAEs
 - Number of TEAEs with Severity \geq Grade 3 Severe
 - Number of Serious TEAEs
 - Number of Study Drug Related TEAEs (Drug Related: A Possibly, Probably or Definitely related TEAE)
 - Number of Entecavir (ETV) Related TEAEs (Drug Related: A Possibly, Probably or Definitely related TEAE)
 - Number of Tenofovir Disoproxil Fumarate (TDF) Related TEAEs (Drug Related: A Possibly, Probably or Definitely related TEAE)
 - Number of TEAEs leading to study drug withdrawal
- TEAE summary by SOC and PT.
- TEAE summary of serious events by SOC and PT.
- TEAE summary by SOC, PT and Severity.
- TEAE summary by SOC, PT and relationship to study drug.
- TEAE summary by SOC, PT and relationship to ETV.
- TEAE summary by SOC, PT and relationship to TD.
- TEAE summary of events leading to the study drug discontinuation by SOC and PT.

All AEs will be listed and will include verbatim term, PT, SOC, treatment, causality to study drug, ETV and TDF, severity, seriousness, outcome, and action taken with regards to the study drug and AE. Separate listings will be created for SAEs and events leading to study drug withdrawal.

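### The SAP gives treatment-emergent AEs a start but no end, and the protocol's 7-day recording limit is ambiguous, so the AE tables may pool 16 weeks on EYP001a/placebo with 24 weeks on NA alone

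*SAP*

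**What the plan says.** **Definition and tables.** SAP 3.2 sets only a starting point: "Treatment Emergent Adverse Events (TEAEs) are defined as adverse events that occurred following the first administration of study medication". SAP 13.1 adds: "All AE summaries will be restricted to TEAEs only". The table list in SAP 18 and the mock shells for Tables 14.3.3.1 to 14.3.3.6 have columns for treatment arm and HBeAg subgroup, with patient counts and event counts, but none for study period.

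**Periods.** SAP 2.1 divides each patient's time into "90 days screening, 112 days (16 weeks) experimental treatment period and 168 days (24 weeks) follow-up on NA standard of care therapy (SOC) only".

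**Recording limit.** Protocol 8.1.1 says that AEs "from the time the participant signed the ICF through 7 days after the last study drug dose will be recorded in the eCRF". Protocol 8.2.2 uses the same limit for serious events.

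**Meaning of study drug.** Protocol 5.11 and Appendix A (footnotes 21 and 22) use the term for EYP001a/placebo together with NA, and 5.11 has patients taking it at home up to Week 40. SAP 13.1 instead tabulates relationship to study drug separately from relationship to ETV and to tenofovir, which implies EYP001a/placebo alone.

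**Schedule.** Protocol 6.2.3 and Appendix A place AE monitoring at Weeks 20, 28 and 40, and Protocol 3.1 calls these 24 weeks a safety follow-up.

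**The concern.** A TEAE table is usually read as what happened on the investigational product. Here the definition lets any event recorded after the first dose into the same cell, whether it began in Week 3 on EYP001a or in Week 35 on NA alone. If the two arms have similar event rates once EYP001a/placebo stops, the follow-up adds the same background to both and pulls ratios towards 1.

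The texts also leave the window open. One programmer could cut AE data near Day 119 and another near Week 41, and each could cite the protocol. With at most 37 and 12 patients and no AE testing planned, these tables are the main AE comparison, so their window should be fixed in advance. SAP 16.1 provides for a database lock on visits to Week 16 followed by unblinding. A split devised after that would be chosen with treatment codes known.

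**Working it through.** **1. The plan's own figure.** Protocol 3.1 and SAP 2.1 give 370 days: 90 + 112 + 168 = 370. This reproduces. Time after first dose is 112 + 168 = 280 days, of which 168/280 = 60% is on NA alone.

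**2. When recording ends.**
- Study drug = EYP001a/placebo only: 112 + 7 = Day 119. Only 7/119 = 5.9% of the window is off EYP001a/placebo.
- Study drug includes NA: 280 + 7 = Day 287, about Week 41. Days beyond Day 119 are 287 − 119 = 168, or 58.5% of 287.

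AE monitoring at Weeks 20, 28 and 40 would have little purpose under the first reading. The second is therefore better supported, though not stated.

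**3. Event-rate ratio.** The documents give no AE rates for this trial, so the on-treatment ratio R is assumed, with equal rates in both arms after Week 16. Pooled to Week 40, the ratio is (112R + 168)/280.

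| Assumed R | Pooled to Week 40 |
|---|---|
| 1.5 | 1.20 |
| 2.0 | 1.40 |
| 3.0 | 1.80 |

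Under the Day 119 reading, R = 2 gives (112×2 + 7)/119 = 1.94, so there is almost no dilution.

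**4. Patient incidence.** Let p be the placebo incidence over 16 weeks, with constant background hazard and an assumed on-treatment hazard ratio of 2. On-treatment incidence on EYP001a is 1 − (1 − p)². Follow-up incidence in either arm is q = 1 − (1 − p)^(168/112). Pooled incidence is 1 − (1 − on-treatment incidence)(1 − q). For p = 10%, EYP001a is 19.0% and q = 14.6%; pooled values are 30.8% and 23.2%.

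| p | Risk ratio, 16 weeks → 40 weeks | Risk difference (points), 16 weeks → 40 weeks |
|---|---|---|
| 5% | 1.95 → 1.37 | 4.8 → 4.4 |
| 10% | 1.90 → 1.33 | 9.0 → 7.7 |
| 30% | 1.70 → 1.21 | 21.0 → 12.3 |
| 50% | 1.50 → 1.11 | 25.0 → 8.8 |

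**5. Event counts.** With equal follow-up rates, the same expected number of events per patient is added to each arm and cancels in the difference. The excess per patient is unchanged. As a second check, take a background of 0.1% per week and an EYP001a excess of 2% per week for 16 weeks (both assumed):
- 16 weeks: (1 − e^−0.336) − (1 − e^−0.016) = 27.0 points.
- 40 weeks: (1 − e^−0.36) − (1 − e^−0.04) = 26.3 points.

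For a rare background event the risk difference barely moves.

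**The case against.** The strongest reply is that the protocol already closes the window. Recording stops 7 days after the last dose of study drug, and if that means EYP001a/placebo, as SAP 13.1 implies, there is almost nothing to dilute. This stands as a possible reading. It does not settle the matter, because Protocol 5.11 and Appendix A include NA in the term and AE checks run to Week 40. For the same reason, a reader should not take 60% off-drug time as established, nor suppose that Protocol 8.1.1 already states an interval tied to EYP001a/placebo.

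A reader might infer that an off-drug liver flare could not be told from an on-drug one. The planned outputs do not support that. Listings 16.2.7.1 to 16.2.7.3 carry start and end dates, liver chemistry is summarised by visit and plotted by patient (SAP 13.2), and pruritus scores are summarised by time point (SAP 13.5). Gastrointestinal events have no by-visit summary but are dated in the listing.

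A reader might also infer that the tables fail the safety objective. That objective is "To explore the safety profile of EYP001a treatment in combination with NA" and names no 16-week limit. Counting events after stopping is a defensible, inclusive rule, and delayed or withdrawal effects of EYP001a would be genuine effects, not dilution. This part of the reply stands. It argues for keeping the overall table, but a separate follow-up table would show such effects more clearly than pooling does.

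**Conclusion.** The point holds as a gap in definition with a conditional effect. The SAP's TEAE rule has no end, no AE table separates the periods, and the protocol's 7-day limit can be read two ways that differ by 168 days. On the longer, better supported reading, and if rates after Week 16 are similar in both arms, relative contrasts shrink: a rate ratio of 2.0 becomes 1.4, and for 10% placebo incidence a risk ratio of 1.90 becomes 1.33. On the shorter reading the effect is negligible.

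It would be too strong to say that absolute contrasts shrink in general. Differences in event counts are unaffected, and risk differences fall materially only for common events. The largest fall in the table, 25.0 to 8.8 points, assumes that half of placebo patients have the event within 16 weeks. With 12 placebo patients planned, one patient is 1/12 = 8.3 points. All these rates are assumptions. AE summaries are descriptive (Protocol 11.3.6; SAP 3.3), so no error rate or power figure is touched. This is a cheap improvement.

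**What to change.** 1. State in the protocol or a clarification letter what study drug means for AE and SAE recording, and reconcile Protocol 8.1.1 and 8.2.2 with Protocol 5.11, Appendix A and SAP 13.1.
2. In SAP 3.2, define on-treatment TEAEs as onset or worsening from the first EYP001a/placebo dose to 7 days after the last EYP001a/placebo dose.
3. Run Tables 14.3.3.1 to 14.3.3.6 for that window and separately for follow-up, and keep the overall table so that late events stay visible.

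The cost is a few sentences and further runs of existing programs. The drawback is more tables to produce and read.

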### 8.1.6. Pre-Existing Medical Conditions

A pre-existing medical condition is one that is present at the start of the trial. Such conditions should be recorded on the Medical History eCRF. A pre-existing medical condition should be recorded as an AE or SAE only if the frequency, severity, or character of the condition worsens during the trial. When recording such events on an SAE Report Form and/or AE eCRF, it is important to convey the concept that the pre-existing condition has changed by including applicable descriptors.

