### 11.3.6. Safety Analyses

Listings and summaries for all safety data will be presented using the Safety Set. Safety endpoints will be summarised by treatment group.

The following data presentations and summaries will be performed. No formal inferential statistics will be performed on safety assessments.

All AEs will be coded using the Medical Dictionary for Regulatory Activities (MedDRA®). All AE summaries will be restricted to TEAEs only and will be summarised by treatment group. Summary tables will include the number of patients (%) experiencing an event and the number of events. Patients will be counted only once at each system organ class and preferred term (PT) level of summary.

The TEAE summaries may include but not be limited to:

- TEAE summary by SOC and PT
- TEAE summary of serious events by SOC and PT
- TEAE summary by severity by SOC and PT
- TEAE summary by causality by SOC and PT

All AEs will be listed and will include verbatim term, preferred term (PT), system organ class, treatment, severity, causality, seriousness, and action taken with regards to the study drug. Separate listings will be created for SAEs and events leading to treatment discontinuation.

Clinical laboratory results will be summarised by treatment group and will include changes from baseline and counts of number of values out of normal range at each scheduled time point. Shift tables (categorical parameters) may also be used, as appropriate. Individual vital signs assessments will be listed for each patient. Summaries of vital signs by treatment group will include changes from baseline for each parameter at each scheduled time point.

Individual ECG results will be listed for each patient. Summaries of ECGs by treatment group will include changes from baseline for each parameter at each scheduled time point.

Physical examination findings will be listed for each patient and any changes described in the text of the final report.

Exposure to study drug and concomitant medications will be listed by patient and coded using the most current WHO drug dictionary available at the Sponsor. The number and percentage of patients who used prior and/or concomitant medications will be summarised by Anatomic Therapeutic Chemical (ATC) classification levels and treatment group. At each level of ATC classification, patients will be counted once. Concomitant medications

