3.5 Handling of Missing Data

For the classification of Treatment emergent adverse event (TEAE) and Concomitant medication, the following will be applied in the following order:

- a. If all dates/times (start and stop) missing, the event/medication will automatically be classified as a TEAE/Concomitant medication.
- b. For AEs with a missing start date/time, if the event end date/time is prior to first study drug administration, the event will not be classified as a TEAE.
- c. If only the AE start year/ medication end year is present and is the same or is after the first study drug administration year unit, the event/medication will be classified as a TEAE/Concomitant medication.
- d. If the AE start month and year/medication end month and year are present and are the same or after the first study drug administration month and year units, the event/medication will be classified as a TEAE/Concomitant medication.

For the efficacy analysis of values that are below the LLOQ, the following imputations will be made for continuous data analyses:

- HBsAg LLOQ/TND values will be set to $0.015[\log_{10}(0.015) = -1.852]$
- HBsAg LLOQ/TD values will be set to the midpoint between LLOQ/TND and LLOQ/TD.
- HBV DNA LLOQ/TND values will be set to 10 ($\log_{10}(10) = 1$).
- HBV DNA LLOQ/TD ($< 1.30 \log \text{ IU/mL}$) values will be set to the midpoint of LLOQ/TND (the midpoint = 1.15)
- HBV DNA = “insufficient sample” will be set to missing.
- HBcrAg LLOQ/TND values will be set to 30 ($\log_{10}(30) = 1.5$).

- HBcrAg LLOQ/TD (<3.0 log U/mL) values will be set to 2.25 (log U/mL)
- HBcrAg = “insufficient sample” will be set to missing.
- HBV-pgRNA = “insufficient sample” will be set to missing.
- HBV-pgRNA LLOQ/TND values will be set to 100 ($\log_{10}(100) = 2$).
- HBV-pgRNA values = “<4.04” will be set to 3.02 log C/mL
- HBV-pgRNA LLOQ/TD values will be set to the midpoint of LLOQ/TND (the midpoint = 3.02 log C/mL)

For the handling of missing primary efficacy data (excluding LLOQ/TND and LLOQ/TD), missing primary efficacy data (HBsAg) will be imputed using multiple imputation process (MI SAS procedure) with MAR pattern. For completeness, analysis will be repeated under the scenario of no imputation.

The Multiple imputation will be performed as follows:

- Missing data will be imputed using multiple imputation technique with Markov chain Monte Carlo method assuming MAR and multivariate normality.

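### The TEAE definition has no worsening clause, so an adverse event that starts in screening, worsens on treatment and stays one record is missing from every AE summary table

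*SAP*

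**What the plan says.** SAP 3.2 gives the only TEAE definition in the two documents: "Treatment Emergent Adverse Events (TEAEs) are defined as adverse events that occurred following the first administration of study medication". The AE table shells (14.3.3.1 to 14.3.3.6) carry the same sentence as a footnote. Neither place mentions an event that began earlier and then got worse.

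The tables depend on that flag. SAP 13.1 states "All AE summaries will be restricted to TEAEs only", and Protocol 11.3.6 agrees: "All AE summaries will be restricted to TEAEs only and will be summarised by treatment group".

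Collection starts well before first dose. Protocol 8.1.1 has AEs recorded "during the period starting from the time the participant signed the ICF through 7 days after the last study drug dose", and Protocol 3.1 says "Patient screening will occur no more than 90 days prior to the Day 1 visit".

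Two other rules bear on the point. SAP 3.5 sets the flag when dates are missing or partial; its last rule begins "If the AE start month and year/medication end month and year are present and are the same or after the first study drug administration". Protocol 8.1.6 deals with conditions already present when the trial starts: such a condition "should be recorded as an AE or SAE only if the frequency, severity, or character of the condition worsens during the trial".

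**The concern.** AEs can be recorded for up to three months before the first dose of EYP001a/placebo, but for a fully dated event the flag that admits it to the tables looks only at whether it began after that dose. Events starting in screening are plausible: Protocol 4.1 (footnote) lets patients be switched to entecavir or tenofovir during this period.

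TEAEs are a declared safety endpoint. Protocol 5.7 names pruritus and raised hepatic enzymes among the possible drug-related effects. Protocol 5.4 reports pruritus in 15 of 24 subjects in EYP001-202, with three Grade 3 episodes and five leading to early treatment termination. If mild itch begins in screening and becomes severe on drug, the AE tables by severity, relationship and discontinuation are where a reader would look for it. SAP section 18 sends most of these tables to both scheduled DSMC reviews.

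**Working it through.** No sample size, power or alpha is involved, so the check applies the rules as written and then sizes one missed patient.

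**Tracing one event.** Take an AE of Grade 1 with a complete start date of Day -30 that becomes Grade 3 on Day 20 and stays one record.

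1. It is recorded, because Protocol 8.1.1 starts at consent. Day -30 lies within the 90-day screening period, and that figure agrees with the stated total engagement: 90 + 112 + 168 = 370 days.
2. It is not a TEAE under SAP 3.2, because it did not begin after first dose. SAP 3.5 does not apply, because its dates are complete.
3. It is excluded from Tables 14.3.3.1 to 14.3.3.6 by SAP 13.1 and Protocol 11.3.6.
4. It remains in Listing 16.2.7.1, and in 16.2.7.2 or 16.2.7.3 if serious or leading to withdrawal. The 16.2.7.1 shell has one start date and one severity per record, so the grade change has no date of its own.

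A new Grade 1 event on Day 5 would be a TEAE. The milder event is counted and the worse one is not.

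**Where the trace changes.**

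- *Missing or partial dates (SAP 3.5).* Rule a makes an event with no dates a TEAE. Rule b uses the end date when the start is missing. Rules c and d make an event dated only to the year or month of first dose a TEAE, even if it began in screening. These rules lean towards inclusion, so the omission is exact only for complete start dates.
- *Condition present at the start of the trial (Protocol 8.1.6).* Its worsening becomes an AE and, if dated at the worsening, is a TEAE under the current definition. If the start means consent, this covers conditions present before consent and leaves a gap for onset between consent and first dose. If it means Day 1, the gap may close. Protocol 8.1.1 points to consent. The screening visit list (6.2.1) and the schedule (Appendix A), which mark AE monitoring only from Treatment Visit 1, point to Day 1.

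**Size.** The documents give no rate for AEs open at first dose or for worsening.

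- Planned active arm: 37 patients, so one patient is 1/37 = 2.7%.
- SAP 15 says enrolment was suspended after about 25 randomisations. At 3:1 this is 25 × 3/4 = 18.75, about 19 active patients, and one patient is 1/19 = 5.3%.
- Illustration only: assume 10–20% of active patients have an AE open at first dose and 10–25% of those worsen. The expected number is 19 × 0.10 × 0.10 = 0.19 to 19 × 0.20 × 0.25 = 0.95. With 37 patients it is 0.37 to 1.85. This covers all AE types, and assumes that each worsening stays on the original record.

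**The case against.** The strongest reply is that the loss is conditional. It needs the site to keep the worsening on the original record, and neither document requires that. A site that treats Day 1 as the start of the trial would follow Protocol 8.1.6 and enter a post-dose AE, which the present definition already counts. This stands, and it rules out saying that such events are always lost. It does not remove the point: Protocol 8.1.1 starts recording at consent, the start of the trial is undefined, and no onset date is prescribed for the worsening.

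The second reply is that the signals appear elsewhere. All AEs are listed, and the listings go to both scheduled DSMC reviews. Table 14.3.4.4 gives maximum CTCAE grade for ALT, AST, bilirubin and GGT; there are laboratory change and shift tables, and VAS and 5-D itch tables. This also stands. A reader might infer that liver or itch worsening would be hidden, and the documents do not support that. But those tables carry no AE relationship, seriousness or discontinuation attribution. SAP section 18 leaves Table 14.3.4.4 out of the first DSMC package and the 5-D table out of both.

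Third, a liver-enzyme AE already open at first dose should be rare. Inclusion criterion 6a requires both baseline ALT or AST measurements at or below 2 × ULN, exclusion criterion 5 removes confirmed rises above that, and Protocol 8.1.5 limits when a laboratory result is an AE. This is fair.

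A reader might also infer that undercounting falls mainly on the active arm. That is plausible for a drug effect, but the documents give no rates by arm, so it cannot be asserted.

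**Conclusion.** The definition is incomplete and should be corrected. An AE with a complete start date before first dose that worsens on treatment, and is kept as one record, is left out of every AE summary table. It is not lost from the study. Whether the worsening is captured in the tables depends on how each site reads Protocol 8.1.6 against 8.1.1, and a declared safety endpoint should not rest on that.

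The number of patients affected is unknown and probably small: below one expected active patient under the assumed rates with 19 active patients. In an arm of that size a single missed patient still moves an incidence by about 5 percentage points.

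**What to change.** In SAP 3.2 and the footnotes to Tables 14.3.3.1 to 14.3.3.6, define a TEAE as an AE with onset at or after the first dose of EYP001a/placebo, or with onset before that dose and an increase in severity, frequency or seriousness after it. A change in assessed relatedness alone is not worsening and should not be part of the clause.

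State alongside it that such a worsening is entered as a new AE record dated at the change. Both parts are needed: without a dated record the programmer cannot tell when the event worsened. Only the post-dose record should carry the flag, because the tables count events as well as patients.

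The cost is one sentence, the footnotes and an eCRF completion note, with a few more AE records. No design, dose or clinical rule changes.
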